2.3. Study Design

Overview of Study Design and Key Features	
Part A Healthy Volunteers 1 ^o :Safety +Tolerability 2 ^o : PK (0.2%-20% BSA) Exploratory: PD: Skin Prick Test: - Weal and flare (D1, D3, D7) Duration of response effect (D7) Each strength N=9	Part B Cold Urticaria Patients (N=12) 1 ^o : Safety +Tolerability 2 ^o : PK (~5% BSA) Exploratory: PD: SPT Weal and flare (D1, D3) Cold temperature test (D1, D3) Maximum tolerated strength
Key: PD – Pharmacodynamics PK – Pharmacokinetics BSA – Body Surface area SPT – Skin prick test 1 ^o - Primary objective 2 ^o - Secondary Objective	Part C Chronic Spontaneous Urticaria (N=12) 1 ^o : Safety +Tolerability 2 ^o : PK (~ 20% BSA) Exploratory: PD (weal, flare, itch D1-D7) Quality of Life Maximum tolerated strength
Design Features	
 This is a randomized double blind (sponsor unblinded), single, bilateral and repeat ascending dose First Time in Human study designed to evaluate the safety, tolerability, pharmacokinetics and pharmacodynamics of GSK2646264 or matching placebo conducted in three parts: Part A (healthy subject cohort, inpatient), Part B (cold urticaria subject cohort, inpatient) and Part C (chronic spontaneous urticarial subject cohort, outpatient).
Dosing	
 There will be a 7-28 day period from screening to admission to the clinic on Day -1. Subjects randomised on Day -1 in Part A and B and on Day 1 in Part C of study. Dosing will start on Day 1. The cream will be applied at 10 mg/cm² for all doses but the dose escalation is based on both increase in cream strength (0.5 % strength for Group 1 Part A; and if data permits 1.0% strength for Group 2 Part A), and increase in surface area of the body on which the cream will be applied. The escalation based on body surface area (BSA) starts at 0.2% BSA, then 1%, then 5% BSA, then 10% BSA,. For the study, the total BSA has been chosen as 1.8 m² and will not be measured individually, so the surface area on which the cream is applied is similar for all subjects as follows, regardless of their weight and height. All weights of cream are nominal and any one dose will not exceed 40 g.
Treatment Assignment	
 Subjects will participate in the study if they fulfil the eligibility criteria at the time of screening and prior to randomisation for the relevant cohort for which they are assessed. This is the first clinical application for GSK2646264 in any formulation and therefore first exposure in each part of the study will enroll 1 sentinel subject for: 
 Part A dosing group1

Overview of Study Design and Key Features	
	
 ○ Part A dosing group 2 ○ Part B ○ Part C 
Each sentinel subject will be dosed at least 1 day before any other subjects of their dosing group or cohort.
 
 ● Subjects will be assigned to treatment in accordance with the randomization schedule using IVRS system. Randomisation will occur within each cohort of study. Each subject will be randomised to receive bilateral treatment of GSK2646264 or placebo. Randomisation will assign active and placebo to specified areas on left or right side of the body. The left or right side assignment of treatment always refers to the subject's left or right.
Interim Analysis Informal data review	
 ● No formal interim analyses are planned. ● An informal summary of the safety, tolerability, PK and PD data from Part-A will be performed once all subjects are recruited and completed all visits.

2.4. Statistical Hypotheses

The primary focus of the statistical analysis is to describe safety and characterize the preliminary pharmacokinetics of GSK2646264 through estimates of parameters and their variability. Thus, an estimation approach will be taken and 95% confidence intervals will be constructed to provide a plausible range of values, where appropriate, with no formal hypothesis testing. Sample size estimations and results of succeeding sensitivity analyses are given in 9.2 of the protocol.

3. PLANNED ANALYSES

3.1. Interim Analysis (Informal Data review)

No formal interim analyses are planned.

Analysis	Definition / Criteria Analyses Evaluated
During the study	There will be ongoing data reviews conducted by the study team of the unblinded safety and pharmacodynamic data, and any available pharmacokinetic data throughout the trial progression.
Dose Escalation	Dose escalation meetings will be performed as stated in the protocol. At the end of dosing group 1 in Part A, the decision to proceed to the next higher strength and dose for dosing group 2 will be made by the SMC based on a safety report from the PI or designee, on the clinical safety, tolerability, up to and including the follow up visit, and pharmacokinetic exposure up to 24 hours after the last dose, in at least 6 subjects at the highest dose level. The GSK review team will be unblinded to the randomisation code and will usually include the GSK pharmacokineticist, GSK statistician, GSK data management, GSK medical monitor, GSK study team leader, GSK Global Clinical Safety and

Analysis	Definition / Criteria Analyses Evaluated
	Pharmacovigilance and GSK Clinical Matrix Team leader.
Part A Completion	A summary of the safety, tolerability, PK and PD data from Part-A will be performed once all subjects are recruited and completed all visits. This summary will include PK and PD data from Part-A of study cohort. All safety data including adverse events, tolerability, laboratory tests, ECGs and vital signs will be reviewed. The decision to proceed to Part B and C will be made by the investigator and the GSK SMC review team based on assessment of safety and pharmacokinetic data of the studied doses.

The Investigator or designee, study coordinators and any other unit staff who have been involved in assessing subjects will remain blinded during the study; however, they will attend the start of each review meeting to update the GSK team on safety and tolerability summary from each cohort; these team members will not be part of the unblinded dose escalation discussions. The investigator and/or designee should send the relevant data to the GSK review team prior to the meeting of the Safety Monitoring Committee (SMC). The study monitor will remain blinded.

The Safety Monitoring Committee (SMC) will consist of the GSK review team and the Investigator and/or designee. (See Section 5.5. of the protocol for further information)

3.2. Final Analyses

The final planned primary analyses will be performed after the completion of the following sequential steps:

1. All subjects have completed (including for those subjects who withdrew or were withdrawn) the study as defined in the protocol.
2. All required database cleaning activities have been completed and final database released.
3. All criteria for unblinding the randomisation codes have been met.
4. Randomisation codes have been distributed according to procedure.
5. Database freeze has been declared by Data Management

4. ANALYSIS POPULATIONS

Population	Definition / Criteria	Analyses Evaluated
Safety Population	Comprise of subjects who receive at least one dose of study medication.	Study Population Safety
Pharmacokinetic (PK) Population	Comprise of all randomised subjects of the Safety Population for whom a pharmacokinetic sample was obtained and analysed.	PK-Analyses
Pharmacodynamic (PD) Population	Comprise of all randomised subjects of the Safety Population for whom a pharmacodynamic measurement sample was obtained and analysed. Analysis will be based on the actual treatment the subject received for the assigned area	PD -Analyses
Per-Protocol Population	
 Comprise of all PD population subjects who receive at least one dose of study treatment and who comply with the protocol. Protocol deviations that would exclude subjects from the PP population are defined in Appendix 1 (Protocol Deviation Management Plan) for Definition Per-Protocol Population). 	As required for PD-Analyses

NOTES :

- Please refer to [Appendix 10](#): List of Data Displays which details the population to be used for each displays being generated.

4.1. Protocol Deviations

- Important protocol deviations (including deviations related to study inclusion/exclusion criteria, conduct of the trial, patient management or patient assessment) will be summarised and listed.
- Important deviations which result in exclusion from the analysis population will also be summarised and listed. (Please refer to [Appendix 1](#): Protocol Deviation Management and Definitions for Per Protocol Population]).
- Protocol deviations will be tracked by the study team throughout the conduct of the study in accordance with the Protocol Deviations Management Plan.
 - Data will be reviewed prior to unblinding and freezing the database to ensure all important deviations and deviations which may lead to exclusion from the analysis are captured and categorised in the protocol deviations dataset.
 - This dataset will be the basis for the summaries and listings of protocol deviations.

- A separate summary and listing of all inclusion/exclusion criteria deviations will also be provided. This summary will be based on data as recorded on the inclusion/exclusion page of the eCRF.

5. CONSIDERATIONS FOR DATA ANALYSES AND DATA HANDLING CONVENTIONS

- There are no planned examination of covariates and subgroups.
- There are no planned adjustments made for multiple centres in this study.
- There are no planned adjustments for multiple comparisons or multiplicity.

Table 1 provides an overview of appendices within the RAP for outlining general considerations for data analyses and data handling conventions.

Table 1 Overview of Appendices

Section	Component
11.1	Appendix 1 : Protocol Deviation Management and Definitions for Per Protocol Population
11.2	Appendix 2 : Time & Events
11.3	Appendix 3 : Data Display Standards & Handling Conventions
11.4	Appendix 4 : Derived and Transformed Data
11.5	Appendix 5 : Premature Withdrawals & Handling of Missing Data
11.6	Appendix 6 : Values of Potential Clinical Importance
11.7	Appendix 7 : Examination of Covariates, Subgroups & Other Strata
11.8	Appendix 8 : Model Checking and Diagnostics for Statistical Analyses.
11.9	Appendix 9 : Abbreviations & Trade Marks
11.10	Appendix 10 : List of Data Displays
11.11	Appendix 11 : Example Mock Shells for Data Displays

6. STUDY POPULATION ANALYSES

6.1. Overview of Planned Analyses

The study population analyses will be based on the Safety population, unless otherwise specified.

Table 2 provides an overview of the planned study population analyses, with full details of data displays being presented in [Appendix 10](#): List of Data Displays.

Table 2 Overview of Planned Study Population Analyses for Part A, B and C of study

[Endpoint / Parameter / Display Type]	Data Displays Generated		
	Table	Figure	Listing
Randomisation			
Randomisation			Y
Disposition			
Subject Disposition	Y		
Investigational Product Status	Y		
Reasons for screen failure			Y
Reasons for withdrawals			Y
Important Protocol Deviations	Y		Y
Deviation leading to exclusion from PP population			Y
Inclusion and exclusion criteria deviation			Y
Study Population	Y		
Demographics			
Demographic Characteristics	Y		Y
Race and Racial Combinations	Y		Y
Medical History			
Medical History	Y		Y
Concomitant Medication			
Concomitant Medication	Y		Y

NOTES :

- Y = Yes display generated.

7. PRIMARY STATISTICAL ANALYSES

7.1. Safety Analyses

7.1.1. Overview of Planned Analyses

The safety analyses will be based on the ‘Safety’ population, unless otherwise specified.

Table 3 provides an overview of the planned analyses, with further details of data displays being presented in [Appendix 10: List of Data Displays](#).

Table 3 Overview of Planned Safety Analyses for Part A, B and C of study

Endpoint / Parameter/ Display Type	Absolute				Change from Baseline			
	Summary		Individual		Summary		Individual	
	T	F	F	L	T	F	F	L
Drug Exposure								
Exposure to Study Drug	Y				Y			
Adverse Events								
Summary of All Adverse Events	Y				Y			
Drug-Related Adverse Events	Y							

Endpoint / Parameter/ Display Type	Absolute				Change from Baseline			
	Summary		Individual		Summary		Individual	
	T	F	F	L	T	F	F	L
Summary of All Localised Adverse Events	Y							
Serious Adverse Events	Y			Y				
AEs Leading to Discontinuation	Y			Y				
AE by Maximum Intensity	Y							
Clinical Laboratory Assessments								
Clinical Chemistry	Y			Y	Y			Y
Haematology	Y			Y	Y			Y
Urinalysis	Y			Y ¹	Y			
Electrocardiogram (ECG)								
ECG Findings	Y			Y	Y			Y
ECG Values	Y			Y	Y			Y
Vital Signs								
Vital Signs	Y			Y	Y			Y
Tolerability assessment								
Tolerability scores	Y			Y	Y			Y

NOTES :

- T = Table, F = Figure, L = Listing, Y = Yes display generated.
- Stats Analysis = Represents TFL related to any formal statistical analyses (i.e. modelling) conducted.
- Summary = Represents TFL related to any summaries (i.e. descriptive statistics) of the observed raw data.
- Individual = Represents FL related to any displays of individual subject observed raw data.
- Tolerability analyses will be produced for Part A and B only.

1 Urinalysis will only list abnormal assessments

7.1.1.1. Dose Escalations

The principal investigator and study monitor will provide a report of findings during the last treatment for progressing to the next cohort, as defined in the protocol, but remain blinded. As required, ongoing data reviews will be conducted by the unblinded GSK study team throughout the trial progression.

8. SECONDARY STATISTICAL ANALYSES**8.1. Pharmacokinetic Analyses**

The pharmacokinetic (PK) analyses will be based on the Pharmacokinetic population, unless otherwise specified.

Table 4 provides an overview of the planned analyses, with full details being presented in Appendix 10: List of Data Displays

Table 4 Overview of Planned Pharmacokinetic Analyses for Part A, B and C of study

Endpoint / Parameter/ Display Type	Untransformed								Log-Transformed							
	Stats Analysis			Summary		Individual			Stats Analysis			Summary		Individual		
	T	F	L	T	F	F	L	T	F	L	T	F	F	L		
Pharmacokinetics																
PK concentrations				Y	Y	Y	Y								Y	
PK parameters				Y			Y						Y			

NOTES :

- T = Table, F = Figure, L = Listings, Y = Display generated.
- Stats Analysis = Represents TFL related to any formal statistical analyses (i.e. modelling) conducted.
- Summary = Represents TFL related to any summaries (i.e. descriptive statistics) of the observed raw data.
- Individual = Represents FL related to any displays of individual subject observed raw data.

8.1.1. Drug Concentration Measures

Refer to [Appendix 4](#): Data Display Standards & Handling Conventions (Section [11.3.3](#) Reporting Process & Standards).

8.1.2. Pharmacokinetic Parameters**8.1.2.1. Deriving Pharmacokinetic Parameters**

- Refer to Appendix : Data Display Standards & Handling Conventions (Section [11.3.3](#) Reporting Process & Standards).
- The pharmacokinetic parameters will be calculated by standard non-compartmental analysis according to current working practices and using Phoenix WNL v6.3.
- All calculations of non-compartmental parameters will be based on actual sampling times.
- Pharmacokinetic parameters described in [Error! Reference source not found.](#) Table [5](#) will be determined from the plasma concentration-time data, as data permits.

Table 5 **Derived Pharmacokinetic Parameters**

Parameter	Parameter Description
AUC(0-t)	Area under the concentration-time curve from time zero to the time of the last quantifiable concentration (C(t)) will be calculated using the linear trapezoidal rule for each incremental trapezoid and the log trapezoidal rule for each decremental trapezoid.
AUC(0-24)	Area under the concentration-time curve from time zero to 24 hours after dosing
AUC(0-∞)	Area under the concentration-time curve extrapolated to infinity will be calculated as: $AUC = AUC(0-t) + C(t) / \lambda_z$
%AUCex	The percentage of AUC (0-∞) obtained by extrapolation (%AUCex) will be calculated as: $[\text{AUC}(0-\infty) - \text{AUC}(0-t)] / \text{AUC}(0-\infty) \times 100$
Cmax	Maximum observed concentration, determined directly from the concentration-time data.
Tmax	Time to reach Cmax, determined directly from the concentration-time data.
t½	Apparent terminal half-life will be calculated as: $t_{1/2} = \ln 2 / \lambda_z$

NOTES:

- Additional parameters may be included as required.
- Lambda z is the terminal phase rate constant.

8.1.2.2. Statistical Analysis of Pharmacokinetic Parameters

All the derived parameters described above will be listed. The first point, last point and number of points used in the determination of λ_z will be included on the listing of the derived parameters. For each of the PK parameters, except t_{max} and $\%AUC_{\infty extrap}$, the following summary statistics will be calculated for each active treatment group: median, maximum, minimum, arithmetic mean, standard deviation, coefficient of variation, geometric mean, 95% confidence interval for the geometric mean and standard deviation of logarithmically transformed data. For t_{max} and $\%AUC_{\infty extrap}$, median, maximum, minimum, arithmetic mean and standard deviation will be calculated. All statistical analysis results of these PK parameters will be presented in relation to the actual dose given (i.e. the BSA covered)

9. EXPLORATORY STATISTICAL ANALYSIS**9.1. Pharmacodynamic and Biomarker Analyses****9.1.1. Overview of Planned Pharmacodynamic Analyses**

The pharmacodynamic analyses will be based on the ‘Pharmacodynamic’ and Per-protocol populations, unless otherwise specified. All summaries will be presented by treatment group and/or include total column. Figures comparing the different treatments will be displayed overlayed where possible.

- If endpoints are listed, then all data will be listed.

[Table 6](#) provides an overview of the planned pharmacodynamic analyses, with full details of data displays being presented in [Appendix 10: List of Data Displays](#).

Table 6 Overview of Planned Pharmacodynamic Analyses for Part A

[Endpoint / Parameter/ Display Type]	Untransformed														
	Absolute							Percent of Inhibition							
	Stats Analysis			Summary		Individual		Stats Analysis			Summary		Individual		
	T	F	L	T	F	F	L	T	F	L	T	F	F	L	
Allergen Challenge - Part A : Healthy Subjects															
Weal area (mm ²)				Y	Y			Y				Y	Y	Y	Y
Weal volume (mm ³)				Y	Y			Y				Y	Y	Y	Y
Longest Weal diameter (mm)				Y	Y			Y				Y	Y	Y	Y
Weal perpendicular length (Height) (mm)				Y	Y			Y				Y	Y	Y	Y
Flare erythema ((mm ²)				Y	Y			Y				Y	Y	Y	Y

NOTES :

- T = Table, F = Figure, L = Listing, Y = Yes display generated.
- Stats Analysis = Represents TFL related to any formal statistical analyses (i.e. modelling) conducted.
- Summary = Represents TFL related to any summaries (descriptive statistics) of the observed raw data. Summary will be presented by dose strength, BSA and day (if applicable)
- Individual = Represents FL related to any displays of individual subject observed raw data.
- Weal area derived from weal longest diameter and perpendicular length; assuming elliptic shape.

Table 7 Overview of Planned Pharmacodynamic Analyses for Part B

[Endpoint / Parameter/ Display Type]	Untransformed														
	Absolute							Percent of Inhibition/Change ¹							
	Stats Analysis			Summary		Individual		Stats Analysis			Summary		Individual		
	T	F	L	T	F	F	L	T	F	L	T	F	F	L	
Allergen Challenge - Part B: Cold Urticaria Subjects															
Weal area (mm ²)				Y	Y			Y				Y	Y	Y	Y
Weal volume (mm ³)				Y	Y			Y				Y	Y	Y	Y
Weal longest diameter (mm)				Y	Y			Y				Y	Y	Y	Y
Weal perpendicular length (Height) (mm)				Y	Y			Y				Y	Y	Y	Y
Flare erythema ((mm ²)				Y	Y			Y				Y	Y	Y	Y
Cold Temperature Test				Y	Y			Y				Y	Y	Y	Y

NOTES :

- T = Table, F = Figure, L = Listing, Y = Yes display generated.
- Stats Analysis = Represents TFL related to any formal statistical analyses (i.e. modelling) conducted.
- Summary = Represents TFL related to any summaries (descriptive statistics) of the observed raw data.
- Individual = Represents FL related to any displays of individual subject observed raw data.
- Summary will be presented by dose strength, BSA and day (if applicable)

1. Change will be produced for Cold Tem Test endpoint

Table 8 Overview of Planned Pharmacodynamic Analyses for Part C

[Endpoint / Parameter/ Display Type]	Untransformed											
	Absolute						Change from Baseline					
	Stats Analysis			Summary		Individual	Stats Analysis			Summary		Individual
	T	F	L	T	F	F	L	T	F	L	T	F
Pharmacodynamic - Part C: Chronic Spontaneous Urticaria Subjects												
UAS7 score				Y			Y	Y			Y	Y
Angioedema Activity Score (AAS)				Y			Y	Y			Y	Y
UAS7 components (Number of weals, Extent of Itch)				Y			Y	Y			Y	Y

NOTES :

- T = Table, F = Figure, L = Listing, Y = Yes display generated.
- Stats Analysis = Represents TFL related to any formal statistical analyses (i.e. modelling) conducted.
- Summary = Represents TFL related to any summaries (descriptive statistics) of the observed raw data.
- Individual = Represents FL related to any displays of individual subject observed raw data.
- Summary will be presented by dose strength, BSA and day (if applicable)

9.1.2. Planned Pharmacodynamic Statistical Analyses**9.1.2.1. Part C: Chronic Spontaneous Urticaria Subjects**

Planned Statistical Analyses
Endpoint(s)

 • Change from baseline in composite total UAS7 score and components
Model Specification

 • Endpoint will be analysed using paired t test and ANCOVA to compare the treatment groups. • ANCOVA model will be fitted as: Post-Pre dose as response and pre dose as covariate.
Model Checking

 • Refer to Appendix 8: Model Checking and Diagnostics for Statistical Analyses.
Model Results Presentation

 • Estimated treatment difference and 95% confidence intervals will be presented.
Analysis of UAS7 Components

 • Analysis of UAS7 components will be performed similar to total UAS7 composite score • Summary Statistics for each component of UAS7 questionnaire will be provided by visit.
Note:

 • Composite score UAS7 will be derived using key urticaria symptoms (number of weal, Itch/Pruritus). The UAS7 score will be calculated using the summation of the 7 consecutive days sum. • Other questions collected as part of UAS7 questionnaire will be listed.

9.1.2.2. The Angioedema Activity Score (AAS)

Planned Statistical Analyses

Planned Statistical Analyses
Endpoint(s)

 • Change from baseline in total and individual item score
Model Specification

 • Endpoint will be analyzed using paired t test and ANCOVA to compare the treatment groups. • ANCOVA model will be fitted as: Post-Pre dose as response and pre dose as covariate.
Model Checking

 • Refer to Appendix 8: Model Checking and Diagnostics for Statistical Analyses.
Model Results Presentation

 • Estimated treatment difference and 95% confidence intervals will be presented.
Analysis of AAS Components

 • Summary Statistics for each component AAS questionnaire will be provided by visit.
Note:

 • Details of the Angioedema Activity Score (AAS) questionnaire are provided in Appendix 7 of the protocol. Each AAS item will be scored between 0 to 3 and daily total score AAS score will range between 0 and 15. The daily AAS score will be summed up to compute 7-day total scores

9.1.2.3. Relationships between Basophil Histamine Release (BHR) Test and Weal Characteristics

Planned Statistical Analyses
Endpoint(s)

 • Positive BHR Test
Model Specification

 • Endpoint will be analyzed using logistic regression with weal characteristics (i.e. weal length) as covariate to establish the relationship between BHR test and weal characteristics.
Model Checking

 • Refer to Appendix 8: Model Checking and Diagnostics for Statistical Analyses.
Model Results Presentation

 • Odds Ratio and 95% Confidence intervals

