### 2.3.3. Part C: Chronic Spontaneous Urticaria Subjects

Objectives	Endpoints
Exploratory	
Pharmacodynamics as assessed by the Urticaria activity score  Urticaria Activity Score: Assess measures of weal characterisation in CsU subjects within treated area only	Pharmacodynamics as assessed by the Urticaria activity score 
 
Urticaria Activity Score, a composite score using key urticaria symptoms (number of weal, itch/pruritus), to derive change from baseline for the 7 days after dosing
 

To measure of Quality of Life	
 
Dermatology Life Quality Index (DLQI) questionnaire
 

To measure disease activity	
 
Angioedema Activity Score (AAS)
 

Investigate relationships between (basophil histamine release) BHR test and weal characteristics	
 
Relationship of positive BHR test with reduction in number or size of weals
 

Systemic measure of target pharmacology  Determine CD69 expression in an ex vivo blood sample following CD69 stimulation	Systemic measure of target pharmacology 
 
Percent inhibition of CD69 expressing cells in blood samples stimulated with anti-IgM.
 

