Day:	Screening	1	2	3	4	5	6	7	8	Day 10 ( $\pm$ 1 day)	Day 15 ( $\pm$ 1 day)	Follow-up Day 22 ( $\pm$ 1 day)	Notes
AAS	X 		X 	X				13. Screening AAS will be completed for the 7 successive days before Randomisation (Day 1) (on the same days as the UAS7). If there is a lapse in any day prior to Day 1 the subject must complete the full 7 days worth of diary entries again during the screening period. 14. The AAS assessment should be completed pre-dose on those days where dosing occurs					
AE assessment		←		X	→							x	
Tolerability Assessment at pre-dose		X 		X 		X 							15. Tolerability assessment at 1 to 2 hours post-dose
BHR- Basophil Histamine Release Test		X 											16. Two samples to be taken pre-dose
Pharmacokinetic Blood Sample		X 		X 		X 			X 	X 	X 		17. PK blood sample taken at pre-dose and 4hr post dose 18. Sample to be taken on same day as CD69 sample, TSH, free T4, T4, T3 samples and vital signs
Study Treatment Dosing		X		X		X							
Con Meds		←		X	→							x	
Outpatient visit	X	X		X		X		X	x	X	X		

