### **6.5. Pharmacodynamic Measures**

#### **6.5.1. Part A & B**

The following PD measures will be assessed:

- Longest weal diameter (measured by ruler).
- Perpendicular weal length (measured by ruler).
- Weal area (calculated using ellipse shape).
- Weal volume (measured by quantitative volumetric morphometry)
- Flare erythema (measured by Mexameter).

For Part B only, the following PD measure will be assessed

- Change in critical temperature thresholds..

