#### **6.5.2. Part C**

##### **6.5.2.1. Urticaria Activity Score (UAS7)**

For the chronic spontaneous urticaria subjects in Part C, Urticaria activity score (UAS7), a composite endpoint, will be derived using key urticaria symptoms (number of weal, itch/pruritus):

UAS7 components will be captured using a daily diary for 7 days. The daily UAS7 score will be the sum of each key component score. A detail of UAS7 daily diary is provided in [Appendix 3](#). The days on which to record in the UAS7 diary are captured in the T&E Table (Section [6.1.4](#)). On days where dosing occurs, the UAS7 diary will be completed pre-dose.

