11.2.1.4. Part C (Chronic Spontaneous Urticaria Cohort)

Day:	Screening	1	2	3	4	5	6	7	Follow-up	Notes
Visit Window (relative to Day 1)	-28 to -7 days								9-14 days after last dose	
Informed Consent	X									
Demographics	X									
Complete physical	X							X		
Body weight (kg)	X									
Height (cm) without shoes	X									
Brief physical		X						X		
Medical/medication/drug/alcohol history	X									
12-lead ECG ¹	X	X					X	X		1. Triplicate ECG at screening and CV risk factors questionnaire
Vital signs	X	X		X		X		X		
Urine drug/alcohol screen	X	X								

Day:	Screening	1	2	3	4	5	6	7	Follow-up	Notes
Visit Window (relative to Day 1)	-28 to -7 days								9-14 days after last dose	
Pregnancy Test (women) ²	X(S)	X (S/U)							X(S)	2. Pregnancy test will be performed 3 times during screening, serum (S) on day -28, day -7 to -4, and a serum or urine (U) pregnancy test the day of the start of the study prior to dosing and a serum pregnancy test at the follow up visit
HIV, Hep B and Hep C screen	X									
Clinical Laboratory Tests	X	X					X	X		
TSH ³	X									3. TSH test only at screening only
Blood Sample for CD69 expression ¹¹		X ⁹						X ¹⁰		9. Predose 10. 4 hours post dose 11 A decision will be made after Part A on whether samples are taken in Part C
Randomisation	X									
UAS-7 Diary ⁴	X	X	X	X	X	X	X	X		4. Screening UAS7 diary will be completed using 7 successive days before randomisation (day 1). If there is a lapse in any day prior to day 1 the subject must complete the full 7 days worth of diary entries again during the screening period.
QOL (DLQI)	X	X						X		
AAS	X	X	X	X	X	X	X	X		
AE assessment		X ⁸ ←-----→						X		8. Tolerability assessment at pre – and post-dose

CONFIDENTIAL

200196

Day:	Screening	1	2	3	4	5	6	7	Follow-up	Notes
Visit Window (relative to Day 1)	-28 to -7 days								9-14 days after last dose	
BHR- Basophil Histamine Release Test		X ⁵								5. Sample taken predose
Pharmacokinetic Blood Sample ⁶		X			X			X		6. PK blood sample taken at pre-dose sample and 2 and 4hr post dose
Study Treatment Dosing		X	X ⁷	X ⁷	X	X ⁷	X ⁷	X		7. The nurse will visit the subject at home to apply the dose
Outpatient visit	X	X			X			X	X	

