No.	Population	IDSL / TST ID / Example Shell	Title	Programming Notes	Deliverable [Priority]
5.11.	PD	Example Non-Standard_PDT 1 modified based on endpoint.	Angioedema Activity Score (AAS) – Summary Statistics (Absolute and Change from Baseline)	Absolute and Change from Baseline Part C only	SAC [1]
5.12.	PD	Example Non-Standard_PDT 2 modified based on endpoint.	Change from baseline in total Angioedema Activity Score (AAS) – Treatment Comparison	Paired t-Test (95%CI) and ANCOVA to compare treatments groups. Pre-Dose Value as Covariate Part C only	SAC [1]
5.13.	PD	Example Non-Standard_PDT 1 modified based on endpoint.	Dermatology Life Quality Index (DLQI) – Summary Statistics (Absolute and Change from Baseline)	Absolute and Change from Baseline Part C only Sum-Score and Analysis of Subscores	SAC [1]
5.14.	PD	Example Non-Standard_PDT 2 modified based on endpoint.	Change from baseline in total Dermatology Life Quality Index (DLQI) – Comparison Improvement from baseline	Paired t-Test (95%CI) Part C only No treatment comparison involved. Improvement from baseline in Quality Index	SAC [1]

Pharmacodynamic and Biomarker: Tables					
No.	Population	IDSL / TST ID / Example Shell	Title	Programming Notes	Deliverable [Priority]
Biomarker					
5.15.	PD	Example Non-Standard_PDT 1 modified based on endpoint.	Inhibition of CD69 biomarker by strength, BSA and day – Summary Statistics	Part A + C	IA[1],SAC [2]
5.16.	PD	Example Non-Standard_PDT 1 modified based on endpoint.	Relationship between Basophil Histamine (BHR) test and Weal Characteristics	Part C only No treatment comparison involved.	SAC[2]

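### SAP 9.1.2.3 regresses pre-dose BHR status on a weal length that is not defined for Part C, and omits the reduction in weals that the endpoint asks about

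*SAP*

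**What the plan says.** The exploratory endpoint in Protocol 2.3.3 is "Relationship of positive BHR test with reduction in number or size of weals". SAP 2.2 repeats it. The paired objective, in both documents, is broader: to look at how the BHR test relates to weal characteristics.

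SAP 9.1.2.3 names the endpoint as "Positive BHR Test" and the model as "logistic regression with weal characteristics (i.e. weal length) as covariate". The result is an odds ratio with a 95% confidence interval. No time point, change score or treatment term is given. The planned display is Table 5.16 in SAP 11.10.10: Part C only, second priority, marked "No treatment comparison involved", and built from a modified descriptive-statistics shell.

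BHR is sampled once, before the first dose. The footnote in Protocol 6.1.4 reads "16. Two samples to be taken pre-dose"; the one in SAP 11.2.1.4 reads "5. Sample taken predose".

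For weals in Part C, Protocol 6.5.2.1 says "UAS7 components will be captured using a daily diary for 7 days". The diary in Protocol Appendix 3 also asks for the average and the largest weal size, each in bands of under 1 cm, 1 to 5 cm and over 5 cm. SAP 9.1.2.1 builds the UAS7 score from weal number and itch, and only lists the other diary answers.

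**The concern.** An analyst who follows SAP 9.1.2.3 has to find a weal length for Part C subjects, and no Part C variable carries that name. The choice of substitute, its time point and whether it is a level or a change would then be made during programming, possibly with treatment codes known, since the sponsor is unblinded throughout.

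The second difficulty does not depend on how weal length is read. The endpoint concerns a reduction in weals. The model relates BHR status to a weal measurement with no change from baseline. Its odds ratio would say whether subjects with larger weals are more or less likely to be BHR positive, which is a different question from whether BHR status goes with improvement.

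At stake is one exploratory result: whether BHR status is a plausible marker of response to carry into later studies.

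**Working it through.** **Plan's own figure.** None exists for this analysis. The only precision figures, in Protocol Table 10, are for Part A, so there is nothing to reproduce.

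**Step 1. Where each variable is collected.**

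| Variable | Parts A and B | Part C |
|---|---|---|
| Weal length by ruler, after skin prick test | Yes (Protocol 6.5.1; SAP Tables 6 and 7; output Table 5.4, marked A and B) | No skin prick test or ruler measurement in Protocol 6.1.4 or SAP 11.2.1.4; not in SAP Table 8 |
| BHR test | Not scheduled | Day 1, pre-dose only |
| Diary weal number, average size, largest size (bands) | Not scheduled | Screening and dosing period |

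No planned assessment gives both BHR status and weal length, as the documents define it, in the same subject. BHR status and the diary items are both available in Part C.

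**Step 2. Endpoint against model.** The endpoint needs BHR status and a change in weal number or size. The model has BHR status and a weal value. SAP 9.1.2.3 is silent on timing, so there are two ways to fill it in:

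- Screening weals as covariate: both variables precede dosing, so no reduction is involved.
- Post-dose weals as covariate: a status fixed before dosing is regressed on later values, again without a change score.

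Neither gives the stated endpoint.

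**Step 3. How much data an analysis would have.** Protocol 9.2 gives 16 subjects in Part C, so the smaller BHR class has at most 16/2 = 8. The documents do not give the BHR-positive proportion *p*; 20%, 30% and 50% are assumed. Expected positives are 16*p*, and P(3 or fewer) is the sum over k = 0 to 3 of C(16,k) p^k (1-p)^(16-k).

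| Assumed *p* | Expected positives, N = 16 | P(3 or fewer), N = 16 | Expected positives, N = 12 | P(3 or fewer), N = 12 |
|---|---|---|---|---|
| 20% | 3.2 | 0.60 | 2.4 | 0.80 |
| 30% | 4.8 | 0.25 | 3.6 | 0.49 |
| 50% | 8.0 | 0.01 | 6.0 | 0.07 |

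N = 12 is included because the SAP still carries that size for Part C.

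**Step 4. A logistic model on a diary size band.** This was simulated with 10,000 runs per setting, no true association, one three-level size band per subject, and assumed band shares of 30/50/20% or 20/70/10%. Complete or quasi-complete separation, or no variation in the band, occurred in about 2% to 21% of runs at N = 16 and 8% to 33% at N = 12. Runs with only one BHR class come on top, up to 3% and 7%. A 7-day average of the band would have more levels, so these rates apply only to a single-band covariate.

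**Step 5. Whether a treatment-by-BHR term is feasible.** At 3:1 allocation (Protocol 5.4), 16 subjects give 16 x 1/4 = 4 on placebo. The interaction cannot be estimated if all 4 share one BHR status, which has probability p^4 + (1-p)^4:

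- 20%: 0.0016 + 0.4096 = 0.41
- 30%: 0.0081 + 0.2401 = 0.25
- 50%: 0.0625 + 0.0625 = 0.125

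**The case against.** The strongest defence is that SAP 9.1.2.3 is thin rather than wrong. It speaks of weal characteristics and does not mention a ruler. The diary holds weal number and size before and during treatment, so a model can be fitted once the covariate is mapped to a diary item. The objective is worded as a relationship, and with one covariate a logistic regression of BHR status on weal change tests association about as well as the reverse arrangement. Leaving treatment out is a declared choice in Table 5.16, and the treatment effect on weal number is analysed separately under the UAS7 components. The endpoint is exploratory and no hypothesis is tested.

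Much of this stands. A reader might infer that the analysis cannot be fitted at all and that no Part C subject has usable weal data. The documents do not support that: it reads the Part A and B ruler definition into a section that does not state it, and passes over the diary. A reader might also infer that the SAP predicts baseline BHR status from later weals, but no time point is given. Nor should 12 active and 4 placebo subjects pooled in one model be read as the SAP's intention. The SAP was written to protocol amendment 2, with both treatments applied to each subject and 12 subjects in Part C; the parallel 3:1 design with 16 came later.

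What does not stand is that this is only missing detail. Weal length is introduced by *i.e.*, so it is the covariate named rather than one example, and the SAP derives no size variable that could replace it. The reduction is absent on any reading of the section.

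**Conclusion.** The point holds in this form: the named covariate is not a defined Part C variable, and the model contains no change from baseline, so as written it does not address the relationship of BHR status with reduction in weals. Placing BHR status on the left is awkward for this endpoint but would not alone invalidate a test of association.

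The consequence is confined to one exploratory, second-priority table. No figure in the plan is wrong. A diary-based logistic model would be possible but fragile: under the assumed positive rates of 20% to 50%, 16 subjects give 3.2 to 8 expected positives, with separation or a constant covariate in about 2% to 21% of simulated trials. These figures rest on assumed BHR rates and band shares. The mismatch between endpoint and model rests on the text alone.

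**What to change.** In SAP 9.1.2.3, delete weal length and the odds ratio. Define the response as change from the screening baseline to the 7-day post-dose period in the diary weal-number and weal-size items, and name the diary days, because Protocol 2.3.3 and SAP 2.2 word that window differently. State an ordinal scoring rule for the bands.

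Summarise the change descriptively by BHR status: mean with 95% confidence interval overall, and individual values or counts by treatment arm. If a model is wanted, use change as the response with BHR status, baseline and treatment as main effects only. Do not include a treatment-by-BHR interaction; about 4 placebo subjects cannot support one. Align Table 5.16 and its shell.

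The cost is SAP wording, the scoring rule and one shell, using data already scheduled for collection. The downsides are that banded items are coarse measures of change and that the estimates will be imprecise. The edit should be made before the Part C data are analysed.
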